#### 11.3.13. Day 78 (Week T-12)

On Day 78 ( $\pm$  1 day) the patient will receive his/her dose of EZN-2279. The dose may be given at the study site or self-administered by the patient.

#### 11.3.14. Day 85 (Week T-13)

On Day 85 ( $\pm$  1 day) the patient will return to the study site and have the following procedures performed:

- Physical examination
- Height and weight for growth assessment
- Performance status
- Vital Signs
- Safety Lab
  - Hematology

- Chemistry
- Adverse event assessment
- Assessment of infectious complications and hospitalizations
- Assessment of concomitant medications and procedures since last study visit

Blood samples will be obtained 15 to 30 minutes prior to administration of EZN-2279 for:

- dAXP
- Trough ADA activity

The patient will receive his/her dose of EZN-2279 after all procedures and laboratory blood draws have been completed.

If the patient will self-administer the Week T-14 dose of EZN-2279, the dose will be dispensed with a dosing diary card and administration instructions.

#### 11.3.15. Day 92 (Week T-14)

On Day 92 ( $\pm$  1 day) the patient will receive his/her dose of EZN-2279. The dose may be given at the study site or self-administered by the patient.

#### 11.3.16. Day 99 (Week T-15)

On Day 99 ( $\pm$  1 day) the patient will return to the study site and have the following procedures performed prior:

- Adverse event assessment
- Assessment of infectious complications and hospitalizations
- Assessment of concomitant medications and procedures since last study visit

Blood samples will be obtained 15 to 30 minutes prior to administration of EZN-2279 for:

- dAXP
- Trough ADA activity

The patient will receive his/her dose of EZN-2279 after all procedures and laboratory blood draws have been completed.

If the patient will self-administer the Week T-16 dose of EZN-2279, the dose will be dispensed with a dosing diary card and administration instructions.

#### 11.3.17. Day 106 (Week T-16)

On Day 106 ( $\pm$  1 day) the patient will receive his/her dose of EZN-2279. The dose may be given at the study site or self-administered by the patient.

#### 11.3.18. Day 113 (Week T-17)

On Day 113 ( $\pm$  1 day) the patient will return to the study site and have the following procedures performed:

- Physical examination
- Height and weight for growth assessment
- Performance status
- Vital Signs
- Safety Lab
  - Hematology

- Chemistry
- Adverse event assessment
- Assessment of infectious complications and hospitalizations
- Assessment of concomitant medications and procedures since last study visit

Blood samples will be obtained 15 to 30 minutes prior to administration of EZN-2279 for:

- dAXP
- Trough ADA activity

The patient will receive his/her dose of EZN-2279 after all procedures and laboratory blood draws have been completed.

If the patient will self-administer the Week T-18 dose of EZN-2279, the dose will be dispensed with a dosing diary card and administration instructions.

#### 11.3.19. Day 120 (Week T-18)

On Day 120 ( $\pm$  1 day) the patient will receive his/her dose of EZN-2279. The dose may be given at the study site or self-administered by the patient.

#### 11.3.20. Day 127 (Week T-19)

On Day 127 ( $\pm$  1 day) the patient will return to the study site and have the following procedures performed:

- Adverse event assessment
- Assessment of infectious complications and hospitalizations
- Assessment of concomitant medications and procedures since last study visit

Blood samples will be obtained 15 to 30 minutes prior to administration of EZN-2279 for:

- dAXP
- Trough ADA activity

The patient will receive his/her dose of EZN-2279 after all procedures and laboratory blood draws have been completed.

If the patient will self-administer the Week T-20 dose of EZN-2279, the dose will be dispensed with a dosing diary card and administration instructions.

#### 11.3.21. Day 134 (Week T-20)

On Day 134 ( $\pm$  1 day) the patient will receive his/her dose of EZN-2279. The dose may be given at the study site or self-administered by the patient.

#### 11.3.22. Day 141 (Week T-21)

On Day 141 ( $\pm$  1 day) the patient will return to the study site and have the following procedures performed:

- Physical examination
- Height and weight for growth assessment
- Performance status
- Vital Signs
- Safety Lab
  - Hematology

- Chemistry
- Urinalysis
- Other labs – obtained 15 to 30 minutes prior to dosing
  - dAXP
  - Trough ADA activity
  - B-, T-, and NK-lymphocyte subset analysis
  - Quantitative immunoglobulins
  - EZN-2279 antibody titers (i.e., neutralizing and binding antibodies) and anti-PEG antibodies
- Adverse event assessment
- Assessment of infectious complications and hospitalizations
- Assessment of concomitant medications and procedures since last study visit
- Assessment of overall survival

The patient will receive his/her dose of EZN-2279 after all procedures and laboratory blood draws have been completed.

Following completion of assessments and dosing at Week T-21 the patient will enter the EZN-2279 maintenance period.

#### **11.4. EZN-2279 Maintenance Period**

As part of standard clinical care, the following evaluations will be performed during visits approximately every 3 months (13 weeks  $\pm$ 3 weeks) until study completion. For example, based upon the start of EZN-2279 treatment (Day 1, Week T-1), maintenance visits would be scheduled to occur on Weeks 34 (Cycle 1), 47 (Cycle 2), 60 (Cycle 3), 73 (Cycle 4), 86 (Cycle 5), 99 (Cycle 6), 112 (Cycle 7), 125 (Cycle 8), 138 (Cycle 9), 151 (Cycle 10), 164 (Cycle 11), 177 (Cycle 12), 190 (Cycle 13)  $\pm$ 3 weeks from start of EZN-2279 treatment.

The patient will have the following procedures performed at each maintenance visit prior to EZN-2279 dosing:

- Physical examination
- Height and weight for growth assessment
- Performance status
- Vital Signs
- Safety Lab
  - Hematology
  - Chemistry
  - Urinalysis
- Other labs – blood samples will be obtained 15 to 30 minutes prior to dosing for:
  - dAXP
  - Trough ADA activity
  - B-, T-, and NK-lymphocyte subset analysis
  - Quantitative immunoglobulins
  - EZN-2279 antibody titers (i.e., neutralizing and binding antibodies) and anti-PEG antibodies
- Adverse event assessment
- Assessment of infectious complications and hospitalizations
- Review of EZN-2279 administration diary card and returned vials for assessment of treatment compliance
- Assessment of concomitant medications and procedures since last study visit

- Assessment of overall survival

An appropriate supply of EZN-2279 will be dispensed along with a medication compliance diary card. Note that it is not necessary to dispense a full 13 week supply during a maintenance visit; quantities of EZN-2279 dispensed will be at the discretion of the Investigator based upon the patient's proximity to the study site and medication compliance.

### **11.5. Study Completion: End-of Treatment, Completion of Maintenance or End of Study**

At the time of study discontinuation, the following evaluations should be repeated:

- Physical examination
- Height and weight for growth assessment
- Performance status
- Vital Signs
- Safety Lab
  - Hematology
  - Chemistry
  - Urinalysis
- Other labs – blood samples will be obtained for:
  - dAXP
  - Trough ADA activity
  - B-, T-, and NK-lymphocyte subset analysis
  - Quantitative immunoglobulins
  - EZN-2279 antibody titers (i.e., neutralizing and binding antibodies) and anti-PEG antibodies
- Adverse event assessment
- Assessment of infectious complications and hospitalizations
- Assessment of concomitant medications and procedures since last study visit
- Assessment of overall survival

All patients, regardless of the reason for study discontinuation (see Section 9.5.1), should have the above evaluations at the time of study discontinuation, whenever possible. All reasons for discontinuation of study treatment must be documented.

#### **11.5.1. 30-Day Early Discontinuation Follow-up**

For patients who discontinue treatment and the study prior to study completion, the following evaluations for safety will occur at least 30 days after the last dose of study drug (EZN-2279 or Adagen®):

- Physical examination
- Height and weight for growth assessment
- Performance status
- Vital Signs
- Safety Lab
  - Hematology
  - Chemistry
  - Urinalysis
- Adverse event assessment
- Assessment of concomitant medications

Any ongoing drug-related toxicities noted will be followed until a stable clinical endpoint is reached (see Section 10.4.4).

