## 12. ADVERSE EVENTS

### 12.1. Assessment Period

The AE reporting period for this study begins with the first lead-in dose of Adagen® and ends 30 days after the final dose of EZN-2279 (or, for patients who are withdrawn before switching treatment to EZN-2279, 30 days after the final dose of Adagen®).

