### 12.2. Definitions

#### 12.2.1. Adverse Event

An *adverse event* is any untoward medical event associated with the use of a drug in humans, whether or not considered drug related. An adverse event can therefore be any unfavorable and unintended sign (including an abnormal laboratory finding, for example), symptom, or disease temporally associated with the use of a drug and does not imply any judgment about causality.

An untoward medical event which occurs outside the period of follow-up as defined in the protocol will not be considered an adverse event. Worsening of a medical condition for which the efficacy of the study drug is being evaluated will not be considered an adverse event.

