### 13.2.3.5. Safety Data Analysis

Adverse Events and Serious Adverse Events – AEs will be categorized using Medical Dictionary for Regulatory Activities (MedDRA) Version 10.0 or later. The intensity of toxicities will be graded by the Investigator as mild, moderate, or severe as described in Section 12.2.5. Serious Adverse Events (SAEs) will be a subset of the overall AE analysis and may be analyzed in a similar manner.

The calculation of AE incidence will be based on the number of patients per AE category. For each patient who has multiple AEs classified to the same category, that patient will be tabulated under the maximum toxicity intensity for that AE category. The incidence of AEs will be tabulated by MedDRA system organ class and preferred term, as well as by treatment group.

An AE onset between the date of the first dose of study drug and 30 days after the last dose of study drug is considered as a treatment-emergent AE.

- Laboratory Safety Data – Hematology, chemistry, and urinalysis data will be summarized by timepoint of collection and by treatment group. In addition, out-of-normal range values will be listed.
- Other Safety Data – the results of antibodies against EZN-2279, antibodies against Adagen®, and antibodies against PEG will be summarized. The relationships between immunogenicity, PK, and the clinical toxicities will be examined as appropriate.

Concomitant medications and findings in physical examinations will be described textually as recorded in the CRF.

Descriptive statistics of vital signs measurements as well as changes from baseline will be tabulated.

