10.6 Safety Data Handling

For the purposes of AE reporting, three time periods will be defined based upon the onset date of the AE:

- “Pre-treatment AEs” are AEs with onset dates < date of the first dose of Adagen[®] study medication.
- “Treatment-emergent AEs” are AEs with onset dates \geq date of the first dose of study medication and within 30 days following the date of the last dose of study medication.
- “Post-treatment AEs” are AEs with onset dates > 30 days after the date of the last dose of study medication, within study STP-2279-002.

“Pre-treatment” and “Post-treatment” AEs are considered non-treatment-emergent AEs. For AEs with partially missing onset dates, an onset date is imputed as detailed in Section 12 (Programming Specifications). If an AE has a completely missing onset date, it is

counted as a “treatment-emergent” event, unless the stop date is on or before the date of the first dose of study medication.

If relationship to study drug is missing, for analysis purposes it will be assumed to be related to study drug. For AEs which occur more than once within a time period (see above), the AE which is most related to study drug in that time period will be used in the summary of AEs by categories of relationship to study drug. Similarly, the AE with the maximum intensity in that time period will be used in the summary of AEs by categories of severity.

For each study drug (EZN-2279 or Adagen[®]) medications will be assigned to a time period as follows:

- Medications taken any time < date of the first dose of Adagen[®] during the Lead-in phase will be considered prior medications.
- Medications can be concomitant with either Adagen[®], EZN-2279, or both. Medications taken any time \geq date of the first dose of respective study medication and within 30 days following the date of the last dose of respective study medication will be considered concomitant medications for that study drug.
- Medications taken > 30 days after the date of the last dose of respective study medication will be considered “post treatment” medications for that study drug.

Note that medications can be counted in more than one category (i.e., prior/concomitant) and can have different assignments for different study drugs. Imputation rules for partially missing start/stop dates are described in Section 12 (Programming Specifications).

Change from baseline to Week X in safety endpoints will be calculated as:

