- The following specifications apply to tables that summarize categorical data unless otherwise noted:
 - Percent of events should be left blank (including the parentheses) if the number of events is zero.
 - If the categories of a parameter are ordered, then all categories between the maximum possible category and the minimum category should be included, even if n=0 for a given category between the minimum and maximum level for that parameter.

- If the categories are not ordered, then only those categories for which there is at least one Patient represented should be included.
- A ‘Missing’ category should be added to any parameter for which information is not available for any patients.
- Missing data should be represented on listings as 1) dashes “-”, and properly footnoted: “ - = data not available” or 2) “N/A”, with footnote “N/A” = Not Applicable”, whichever is appropriate.
- Times should be printed in the format “HH:MM”. “HH” represents the 2-digit hour portion of the time. “MM” represents the 2-digit minute portion of the time. Both hour and minute portions of time are zero-filled on the left if they have only one digit. Missing time portions should be represented on patient listings as dashes (“10:--” and “--:--”). Times that are missing because they are not applicable for the patient should be printed as “N/A” unless otherwise specified.
- Adverse event summary tables will only include treatment-emergent AEs. However, listings will include all AEs (i.e., treatment-emergent and non treatment-emergent AEs) with the non treatment-emergent AEs flagged.

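### A finding dated to an early-discontinuation safety visit after Day 30 falls outside the adverse event reporting period and all adverse event summary tables

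*Protocol*

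**What the plan says.** Protocol 11.5.1 requires a safety visit for patients who leave treatment and the study early. It covers examination, growth, performance status, vital signs, safety laboratory tests, AE assessment and concomitant medications. On timing: "the following evaluations for safety will occur at least 30 days after the last dose of study drug". No upper limit is given.

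Four other places decide what becomes of a finding made there.

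- **Protocol 12.1:** the AE reporting period "ends 30 days after the final dose of EZN-2279", or 30 days after the final Adagen dose for a patient who never switches.
- **Protocol 12.2.1:** "An untoward medical event which occurs outside the period of follow-up as defined in the protocol will not be considered an adverse event".
- **Protocol 13.2.3.5 and SAP 10.6:** an event is treatment-emergent by its onset date. The protocol's limit is "30 days after the last dose of study drug is considered as a treatment-emergent AE" and the SAP's is "within 30 days following the date of the last dose of study medication". SAP 10.6 adds a post-treatment class, whose members "are AEs with onset dates > 30 days after the date of the last dose of study medication, within study STP-2279-002".
- **SAP 11:** "Adverse event summary tables will only include treatment-emergent AEs". It continues: "However, listings will include all AEs (i.e., treatment-emergent and non treatment-emergent AEs) with the non treatment-emergent AEs flagged".

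**The concern.** The visit is there to check safety in patients who stopped early, yet a site that follows 11.5.1 exactly holds it on or after the last day on which an AE counts. Under the SAP, AE tables are also the main summary route for much of what the visit measures. SAP 7.5 sends abnormal vital signs to the AE summaries and only lists the measured values; SAP 7.6 only lists examination data. Protocol 10.4.3 has clinically meaningful laboratory abnormalities reported as AEs once treatment has begun, with no end date. An abnormality found by test, with no earlier symptom, will usually be given the visit date as its onset.

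At stake is whether new abnormalities in early leavers reach the safety summaries of a single-arm study with about six patients. Those who leave before Week T-21 are outside the completer population used for primary efficacy (SAP 4.3 and 6), so safety is much of what they contribute. Early leavers also include anyone who withdraws during the long maintenance period.

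**Working it through.** The plan states no figure to reproduce. The check compares two time windows, in days after the last dose.

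**Inputs**
- Visit window: Day 30 onward, no limit (Protocol 11.5.1).
- AE reporting and treatment-emergent windows after the last dose: up to and including Day 30 (Protocol 12.1 and 13.2.3.5, SAP 10.6).
- Status is set by onset date (Protocol 13.2.3.5, SAP 10.6).

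**Overlap.** [30, no limit) and [0, 30] have Day 30 alone in common.

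**Effect of visit day.** For a visit on day v, days inside = min(v, 30), days outside = max(0, v − 30), share inside = min(v, 30)/v. Visit days after 30 are assumptions, since the plan sets no limit.

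| Visit day v | Finding dated to visit is treatment-emergent? | Days outside | Share of off-drug interval inside |
|---|---|---|---|
| 30 | yes | 0 | 30/30 = 100% |
| 31 | no | 1 | 30/31 = 96.8% |
| 33 | no | 3 | 30/33 = 90.9% |
| 37 | no | 7 | 30/37 = 81.1% |
| 44 | no | 14 | 30/44 = 68.2% |
| 60 | no | 30 | 30/60 = 50.0% |

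Onsets on Days 1 to 30 are inside the window in every row. What changes is the status of a finding dated to the visit itself, and it changes with a one-day slip from Day 30 to Day 31.

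**Following one finding.** Take a clinically meaningful abnormality first seen on Day 37 and dated to that day.
1. Protocol 12.1: after the reporting period.
2. Protocol 12.2.1: not an AE, if the follow-up period it mentions means the 12.1 period; possibly an AE, if it includes the 11.5.1 visit.
3. SAP 10.6: a post-treatment AE.
4. SAP 11: in no AE summary table; in the listings, flagged, if recorded as an AE.

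**Dependence on the date entered.** SAP 10.6 counts an AE with a completely missing onset date as treatment-emergent unless it stopped on or before the first dose. The same Day 37 finding would be tabulated if its onset were left blank and not if the visit date were entered. Neither document says how to date a finding first made at this visit.

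**A second conflict.** SAP 7.3 limits treatment-emergent events to those arising during the respective therapy and gives no 30-day tail. On that wording even a Day 30 finding misses the tables.

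**Weight of one patient.** The safety set is everyone given at least one dose (SAP 4.1). With exactly six treated, one patient is 1/6 = 16.7%. A patient who stops before Week T-21 is replaced (Protocol 9.5.3), so the set is then at least seven: 1/7 = 14.3%, or 1/8 = 12.5% with eight.

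**The case against.** The strongest reply is that the timing is deliberate. A visit at or after Day 30 can collect the whole 30-day window, whereas an earlier visit would miss its end. Because onset decides, an event that began on Day 20 and is first reported on Day 37 is an AE, is treatment-emergent and is tabulated. This stands. A reader might infer that everything first found at the visit is lost; the documents do not support that.

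Nor is the information lost altogether, as a reader might also infer. SAP 7 has all safety data listed, SAP 7.4 has laboratory listings that identify clinically significant results, and SAP 11 flags non-treatment-emergent AEs in the listings. With about six patients, listings are readable case by case. This stands too, but a listing is not a summary, and the AE listing holds only what the site recorded as an AE.

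It is likewise not established that such findings are outside the AE definition. Section 11.5.1 is itself a follow-up visit with an AE assessment, Protocol 7.4.1 counts a 30-day safety follow-up within participation, and SAP 10.6 expects AEs after Day 30. That leaves 12.2.1 ambiguous without repairing 12.1 or the table rule.

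Antibody results are not at risk from this gap: 11.5.1 takes no antibody sample, and the discontinuation visit in 11.5, which does, is separate.

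Finally, a fixed 30-day treatment-emergent window with later events flagged is a legitimate choice. Tying that window to a visit with no latest day would give patients unequal off-drug risk periods. That stands, and the fix respects it.

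**Conclusion.** The concern holds in a limited form. The visit and the AE window meet on Day 30 only. An abnormality dated to a visit on Day 31 or later is outside the reporting period and all AE summary tables, and the protocol and SAP do not agree on whether it is an AE.

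The gap covers only early leavers, only visits after Day 30, and only findings with no known onset by Day 30. How many patients that will be cannot be worked out from the documents. One such patient is 16.7% of the safety set if exactly six are treated, and at most 14.3% if that patient stopped before Week T-21 and was replaced. Efficacy is not affected. The correction is worth making because it is cheap and the visit is already required.

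**What to change.** 1. **Protocol 12.1:** end AE reporting at the later of 30 days after the last dose and the date of the 11.5.1 visit.
2. **Protocol 12.2.1:** refer explicitly to the 12.1 period, so that the definition and the reporting period cannot diverge.
3. **SAP 10.6:** keep the fixed 30-day treatment-emergent window. Add that a finding first made at the 11.5.1 visit with no earlier known onset is dated to the visit.
4. **SAP 10.6 and 11:** add a separate summary row or small table for events first detected at the 11.5.1 visit, giving days since the last dose.
5. **SAP 7.3:** reconcile its treatment-emergent definition with Protocol 13.2.3.5 and SAP 10.6, so that one rule drives the tables.

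The cost is a few sentences in each document and one extra display. The downside is that a few more late, off-drug events are reported; showing them separately keeps them from blurring the on-treatment rates. The visit schedule and procedures stay as they are.

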## 12. ADVERSE EVENTS

### 12.1. Assessment Period

The AE reporting period for this study begins with the first lead-in dose of Adagen® and ends 30 days after the final dose of EZN-2279 (or, for patients who are withdrawn before switching treatment to EZN-2279, 30 days after the final dose of Adagen®).

